2.0 OBJECTIVES

2.1 Primary Objective

To determine whether the addition of concurrent LDFRT to neoadjuvant full dose FOLFOX results in a pCR response rate of at least 35%.

2.2 Secondary Objective

To assure that neoadjuvant concurrent LDFRT-FOLFOX maintains a high rate of pelvic R0 resection compared to standard preoperative chemoradiation and total mesorectal excision surgery.

3.0 ELIGIBILITY

3.1 Inclusion Criteria

- 3.1.1 ≥ 18 years old at diagnosis.
- 3.1.2 ECOG Performance Status 0, 1, or 2.
- 3.1.3 Biopsy-proven diagnosis of rectal adenocarcinoma.
- 3.1.4 Clinical AJCC 7th edition stage T2N1M0, T3N0M0 or T3N1M0 based on physical examination, CT scan chest [or chest x-ray AND CT abdomen or MRI abdomen AND pelvic MRI or endorectal ultrasound \(ERUS\)](#).
- 3.1.5 Preoperative lower gastrointestinal endoscopy (proctoscopy, sigmoidoscopy, colonoscopy) confirming tumor extent as no less than 5 cm and no greater than 12 cm from the anal [canal](#). If endoscopy is not rigid, CT or MRI can be used to indicate location from anal [canal](#).
- 3.1.6 Evaluation by a surgical oncologist, radiation oncologist, and medical oncologist ≤ 28 days prior to registration.
- 3.1.7 Confirmation that the patient is able to undergo a low anterior, sphincter-sparing resection with total mesorectal excision ≤ 28 days prior to registration.
- 3.1.8 In the absence of treatment on a clinical trial, the patient would be recommended to receive neoadjuvant chemoradiation followed by curative intent surgery.
- 3.1.9 The following laboratory values obtained ≤ 14 days prior to registration:
 - Absolute neutrophil count (ANC) $\geq 1500/\text{mm}^3$.
 - Platelet count $\geq 100,000/\text{mm}^3$.
 - Hemoglobin > 8.0 g/dL. May transfuse to meet eligibility.
 - Total bilirubin ≤ 1.5 x upper limit of normal (ULN).
 - SGOT (AST) ≤ 3 x ULN.
 - SGPT (ALT) ≤ 3 x ULN.

- Creatinine $\leq 1.5 \times$ ULN.

3.1.10 Baseline CEA within 14 days of registration

- 3.1.11 Negative serum pregnancy test (B-HCG) within 14 days prior to registration for women of childbearing potential.
- 3.1.12 Did the patient provide study-specific informed consent prior to study entry?
- 3.1.13 Willingness to return to the enrolling medical site for all study assessments.

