5.0 TREATMENT PLAN

Treatment must begin within 14 days of registration.

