5.1 Chemotherapy

Neoadjuvant FOLFOX (5-FU + leucovorin + oxaliplatin)

This regimen will be repeated every 2 weeks for 6 cycles; (1 cycle = 14 days).

Given first: Oxaliplatin 85 mg/m^2 IV in D5W 500 mL over 2 hours, Day 1

Given second: Leucovorin 200 mg/m^2 IV bolus in D5W 250 mL over 2 hours, Day 1

Given third: 5-FU 400 mg/m^2 IV bolus in a syringe given over 5–15 minutes, Day 1, then $2,400 \text{ mg/m}^2$ in 240 mL of 0.9% Sodium Chloride via continuous IV infusion over 48 hours, Days 1–2

Note: Oxaliplatin is administered first, prior to leucovorin; alternatively leucovorin may be administered (via separate infusion containers) concurrently with oxaliplatin.

5.1.1 If necessary to accommodate holidays, patient schedule or other justified circumstance approved by the PI, the schedule may be modified by \pm 3 days.

5.1.2 Chemotherapy dose modification is at the discretion of the treating medical oncologist, although any patient who requires dose modification below dose level -2 will be removed from study participation. There are no restrictions on dose modifications for the sixth cycle of FOLFOX.

5.1.3 Patients who cannot tolerate 6 cycles of FOLFOX or those who require dose modification below dose level -2 or those who are found to be ineligible for the study based on central review of either the baseline or the follow up MRI or those that withdraw consent will receive preoperative combined modality chemoradiation with infusional 5-FU. There are no restrictions on dose modifications for the 6th cycle of neoadjuvant FOLFOX.

5.1.4 Patients receiving oxaliplatin on this study should be counseled to avoid cold drinks, chewing ice chips, and exposure to cold water or air because the sensory neurotoxicity often seen with oxaliplatin appears to be exacerbated by exposure to cold. The period of time during which the patient appears to be at risk for these cold-induced sensory neuropathies is not well documented. Patients should exercise caution regarding cold exposure during the treatment period. Peripheral sensory neuropathies can occur at any time after receiving oxaliplatin therapy.

5.1.5 Concurrent medications are at the discretion of the treating physician.
Current Greenebaum [Comprehensive](#) Cancer Center recommended:
Ondansetron 16 mg PO daily, if patient unable to take orally give 8 mg IV.
Dexamethasone 12 mg PO daily, if; unable to take orally give IV.

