- Grade 3 or 4 myelosuppression and hospitalization resulting from such do not require expedited reporting via CICERO but will be reported in ONCORE and will be submitted as part of study results.
- Other grade 1-4 events that are expected do not require expedited reporting via CICERO, even if they result in hospitalization.
- Grade 4 events that are unexpected and that are at probably related (per UMB IRB definition) to treatment must be reported via CICERO within 5 calendar days per UMB IRB guidelines.
- All new malignancies should be reported to the IRB whether or not they are thought to be related to either previous or current treatment. All new malignancies should be reported, i.e., solid tumors (including non-melanoma skin malignancies), hematologic malignancies, myelodysplastic syndrome (MDS)/acute myelogenous leukemia (AML), and *insitu* tumors. In CTCAE version 4.0, the new malignancies (both second and secondary) may be reported as one of the following:
 - (1) Leukemia secondary to oncology chemotherapy,
 - (2) Myelodysplastic syndrome,
 - (3) Treatment-related secondary malignancy, or
 - (4) Neoplasm other, malignant (grade 3 or 4).Whenever possible, the IRB reports for new malignancies should include, tumor pathology, history of prior tumors, prior treatment/current treatment including duration, any associated risk factors or evidence regarding how long the new malignancy may have been present, when and how the new malignancy was detected, molecular characterization or cytogenetics of the original tumor (if available) and of any new tumor, and new malignancy treatment and outcome, if available.
- All pregnancies and suspected pregnancies occurring in female patients or in the partner of a male patient during therapy or within 28 days after completion of treatment on GCC 1314 must be reported to the IRB. In CTCAE version 4.0, use the event term, "*pregnancy, puerperium, and perinatal condition-other, fetal exposure (grade4)*".
- IRB reports should be amended upon completion of the pregnancy to report pregnancy outcome (e.g. normal, spontaneous abortion, therapeutic abortion, fetal death, congenital abnormalities).
- The IRB report should be amended for any neonatal deaths or complications occurring within 28 days of birth independent of attribution. Infant deaths occurring after 28 days considered to be related to in utero exposure to the agents used in this trial should be reported to the IRB.

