APPENDIX I

GCC 1314 HP-00060641 STUDY SCHEDULE (v. 13March 2017)

Procedures	Prior to study	Chemo-RT Day 1 of each cycle (6 cycles total) (≤ 2 days)	Restaging (3-5 weeks) after completion of chemo-LDFRT	Surgery (6-8 weeks) after completion of chemo-LDFRT
Informed Consent	R			
History and Physical exam	C ^a	C	C	
Performance Status	C	C	C	
Evaluation by Surg Onc, Med Onc, Rad Onc	C ^a		C	
Toxicity Evaluation		C	C	
Weight, BSA	C	C	C	
Height	C			
CBC with differential and platelets	C ^b	C	C	
CMP (Alb, TBili, Ca, Cl, CO2, Creatinine, G, TP, Na, K, BUN, AlkPhos, AST, ALT)	C ^b	C	C	
CEA	C ^b		C	
CT chest or chest x-ray AND CT abdomen or MRI abdomen	C ^a		C	
MRI pelvis with and without contrast or ERUS	C ^a		C	
Endoscopy (proctoscopy, sigmoidoscopy, colonoscopy)	C		C	
Serum pregnancy test B-HCG	C ^b			
PT/INR/PTT			C	
TME path evaluation				C

C = Conventional Care

R = Research

^a ≤ 28 days prior to registration^b ≤ 14 days prior to registration

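### The only scheduled pregnancy test may be 28 days old at the first FOLFOX and pelvic LDFRT dose; repeating it on the Cycle 1 Day 1 bloods would cut that maximum to 2 days

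*Combined protocol and SAP*

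**What the plan says.** Criterion 3.1.11 requires a "Negative serum pregnancy test (B-HCG) within 14 days prior to registration for women of childbearing potential". Section 4.0 defines registration as the day the verifying physician signs the eligibility checklist, so the window is counted from that signature and not from the first dose. Section 5.0 adds: "Treatment must begin within 14 days of registration".

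In Appendix I, the row "Serum pregnancy test B-HCG" has a single mark, in the pre-study column, with the footnote for 14 days or less before registration. Its cells for Day 1, restaging and surgery are empty. The row "CBC with differential and platelets" has the same baseline footnote but is marked again in the column headed "Chemo-RT Day 1 of each cycle (6 cycles total) (≤ 2 days") and at restaging. The metabolic panel follows the same pattern.

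On chemotherapy, Section 5.1 says: "This regimen will be repeated every 2 weeks for 6 cycles; (1 cycle = 14 days"). Section 5.2.4 places LDFRT on Days 1 and 2 of each cycle, so both treatments start on Cycle 1 Day 1.

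The other pregnancy provisions are the exclusion of pregnant or nursing women (3.2.9), the exclusion of patients unwilling to use contraception (3.2.10), and the reporting rule in Section 10.5. That rule covers "All pregnancies and suspected pregnancies occurring in female patients or in the partner of a male patient during therapy" or within 28 days after treatment ends. None of these requires a second test.

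**The concern.** The trial excludes pregnant women, but it verifies that status only once, relative to a date that can fall two weeks before treatment. If a pregnancy began, or became detectable, after the screening sample, no scheduled test would find it before cycle 1. That cycle delivers oxaliplatin 85 mg/m², 5-FU 2,800 mg/m² and 160 cGy to the pelvis. Blood counts and chemistry, which can also change between registration and dosing, are rechecked at Day 1; pregnancy status is not.

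What is at stake is patient and fetal safety. Nothing here bears on the pCR estimate, its confidence interval or the two-stage rule. The point is confined to the first FOLFOX and LDFRT dose.

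**Working it through.** The protocol states no figure for the total gap, so there is none to reproduce. The check adds up its own windows.

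**Inputs**
- Test to registration: at most 14 days (3.1.11; Appendix I, footnote b).
- Registration to start of treatment: at most 14 days (5.0).
- Day 1 blood window: at most 2 days (Appendix I column heading).
- Cycle length 14 days, 6 cycles (5.1).
- Radiation: 40 cGy twice daily on 2 days per cycle, 960 cGy in total (5.2.4).
- 5-FU: 400 mg/m² bolus plus 2,400 mg/m² infusion per cycle (5.1).
- Planned enrolment: 30 patients (14.0).

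**Maximum test age at first dose**
- Now: (test to registration) + (registration to treatment) = 14 + 14 = 28 days.
- With a repeat in the Day 1 window: 2 days.
- Reduction: 28 − 2 = 26 days.

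**Sensitivity.** Section 5.1.1 lets the chemotherapy schedule move by ± 3 days with approval. If that were read as extending the start of Cycle 1, the current maximum would be 28 + 3 = 31 days. The 14-day limit in 5.0 is worded as mandatory, so 28 days is the better reading.

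**Exposure in cycle 1**
- Radiation: 2 fractions × 2 days × 40 cGy = 160 cGy.
- 5-FU: 400 + 2,400 = 2,800 mg/m².

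**What the repeat leaves uncovered** (no holds or schedule shifts)
- Cycle 6 Day 1 falls 5 × 14 = 70 days after Cycle 1 Day 1.
- Age of the last scheduled test at that point: 28 + 70 = 98 days now, and 2 + 70 = 72 days with the repeat.
- Radiation in cycles 2 to 6, with no scheduled test in those cycles: 960 − 160 = 800 cGy.

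**Extra assays**
- Upper bound: one for each of 30 patients = 30.
- The documents give no age or sex distribution. Assuming 10% to 20% are women of childbearing potential: 0.10 × 30 = 3 to 0.20 × 30 = 6.

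**The case against.** The strongest reply is that this is a preference for a tighter window and not a mistake. All baseline laboratory tests are anchored to registration, and 3.1.11, 5.0 and Appendix I agree with one another. That is correct, and the point is made only as an improvement.

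The benefit is expressed as test age and not as risk, and nothing in the documents shows how often a test would approach 28 days or how many pregnancies would be missed. This also stands, and it limits the weight of the point.

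Other provisions lower the risk: the contraception criterion, the history and physical on Day 1 of each cycle, the investigator's discretion under Section 12, and the marking of B-HCG as conventional care, which leaves a clinician free to repeat it. They do lower it, but none is a required test.

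The remedy reaches only 160 of 960 cGy and one of six chemotherapy cycles, and it does not precede the planning CT (5.2.1). This is true. The case for Cycle 1 alone is that it closes the gap between eligibility and first exposure at almost no cost; it does not provide surveillance throughout treatment.

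The instruction in Section 10.5 to code pregnancies as "perinatal condition-other, fetal exposure (grade4") should not be relied on. It is a reporting label that applies to every reported pregnancy, including those of male patients' partners. It does not show that the plan judged its screening interval too long.

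Finally, the Day 1 column heading does not say whether its 2 days run before or after Day 1. The 2-day figure therefore depends on requiring the result before dosing.

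**Conclusion.** The concern holds. The protocol permits a negative B-HCG as old as 28 days at the first FOLFOX and LDFRT dose and schedules no repeat; a required repeat would bring that maximum to 2 days. The 28 days is a worst case resting on a plain reading of 3.1.11 and 5.0. The 2 days rests on drawing the sample no more than 2 days before Day 1 and having the result before treatment. The number of pregnancies this would detect cannot be derived from the documents and is likely to be small. The change is an optional, inexpensive safety improvement with no bearing on the statistical conclusions.

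**What to change.** Leave 3.1.11 as it is, because Section 4.0 requires every eligibility criterion to be met by registration. Add one sentence to Section 5.0 and a footnoted mark, for Cycle 1 only, in the Day 1 column of the Appendix I B-HCG row. Suggested wording: *All women of childbearing potential must have a negative serum B-HCG drawn with the Cycle 1 Day 1 bloods, no more than 2 days before Day 1 and resulted before the first dose of FOLFOX or LDFRT.*

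The cost is one assay per eligible woman on blood already being drawn for the count and chemistry: 3 to 6 assays under the assumed 10% to 20%, and never more than 30. No visit, staff or procedure is added. The one drawback is that a late result could hold up the start of treatment.

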3.2 Exclusion Criteria

- 3.2.1 Clinical T4 tumor.
- 3.2.2 Surgeon indicates the need for an abdominal perineal resection (APR) at baseline.
- 3.2.3 Previous pelvic RT.
- 3.2.4 Autoimmune disease such as scleroderma, lupus, or inflammatory bowel disease.
- 3.2.5 Tumor < 3 mm from the mesorectal fascia as seen on MRI or endorectal ultrasound.
- 3.2.6 Tumor-induced symptomatic bowel obstruction.
- 3.2.7 Chemotherapy (including hormonal therapy) within the past 5 years from date of registration.
- 3.2.8 Other invasive malignancies within past 5 years from date of registration.
- 3.2.9 Pregnant or nursing women.
- 3.2.10 Men or women of childbearing potential who are unwilling to employ adequate contraception.
- 3.2.11 Other co-morbid conditions that, based on the judgment of the physicians obtaining informed consent, would make the patient inappropriate for this study.
- 3.2.12 Any conditions that would preclude a patient from completing all study assessments.

4.0 REGISTRATION

Patients can be registered only after all eligibility criteria are met. The date of registration/enrollment is considered to be the day the Eligibility Checklist is signed by the verifying physician. Once a patient is enrolled, a unique case number will be assigned to the patient in ONCORE.

5.0 TREATMENT PLAN

Treatment must begin within 14 days of registration.

5.1 Chemotherapy

Neoadjuvant FOLFOX (5-FU + leucovorin + oxaliplatin)

This regimen will be repeated every 2 weeks for 6 cycles; (1 cycle = 14 days).

Given first: Oxaliplatin 85 mg/m^2 IV in D5W 500 mL over 2 hours, Day 1

Given second: Leucovorin 200 mg/m^2 IV bolus in D5W 250 mL over 2 hours, Day 1

Given third: 5-FU 400 mg/m^2 IV bolus in a syringe given over 5–15 minutes, Day 1, then $2,400 \text{ mg/m}^2$ in 240 mL of 0.9% Sodium Chloride via continuous IV infusion over 48 hours, Days 1–2

Note: Oxaliplatin is administered first, prior to leucovorin; alternatively leucovorin may be administered (via separate infusion containers) concurrently with oxaliplatin.

5.1.1 If necessary to accommodate holidays, patient schedule or other justified circumstance approved by the PI, the schedule may be modified by \pm 3 days.

5.1.2 Chemotherapy dose modification is at the discretion of the treating medical oncologist, although any patient who requires dose modification below dose level -2 will be removed from study participation. There are no restrictions on dose modifications for the sixth cycle of FOLFOX.

5.1.3 Patients who cannot tolerate 6 cycles of FOLFOX or those who require dose modification below dose level -2 or those who are found to be ineligible for the study based on central review of either the baseline or the follow up MRI or those that withdraw consent will receive preoperative combined modality chemoradiation with infusional 5-FU. There are no restrictions on dose modifications for the 6th cycle of neoadjuvant FOLFOX.

5.1.4 Patients receiving oxaliplatin on this study should be counseled to avoid cold drinks, chewing ice chips, and exposure to cold water or air because the sensory neurotoxicity often seen with oxaliplatin appears to be exacerbated by exposure to cold. The period of time during which the patient appears to be at risk for these cold-induced sensory neuropathies is not well documented. Patients should exercise caution regarding cold exposure during the treatment period. Peripheral sensory neuropathies can occur at any time after receiving oxaliplatin therapy.

5.1.5 Concurrent medications are at the discretion of the treating physician.
Current Greenebaum [Comprehensive](#) Cancer Center recommended:
Ondansetron 16 mg PO daily, if patient unable to take orally give 8 mg IV.
Dexamethasone 12 mg PO daily, if; unable to take orally give IV.

5.1.6 Adjuvant chemotherapy is at the discretion of the treating physician and is not considered part of protocol therapy.

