Low dose fractionated radiation therapy (LDFRT)

Intensity-modulated, bone marrow sparing, whole pelvic radiation therapy
 40 cGy fractions twice per day delivered at least 4–6 hours apart on the first 2 days of each chemotherapy cycle for a total of 6 cycles

	Day 1	Day 2
Oxaliplatin	↓	
Leucovorin	↓	
5-FU	↓	↓
LDFRT	↓↓ (each fraction separated by a minimum of 4 hours)	↓↓(each fraction separated by a minimum of 4 hours)

Primary Objective: To determine whether the addition of concurrent LDFRT to neoadjuvant full dose FOLFOX results in a pCR response rate of at least 35%.

Secondary Objective: To assure that neoadjuvant concurrent LDFRT-FOLFOX maintains a high rate of pelvic R0 resection compared to standard preoperative chemoradiation and total mesorectal excision surgery.

Accrual Goal: 30 patients.

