6.0 RESTAGING

Restaging will take place 4 weeks (± 1 week) after completion of 6 cycles of FOLFOX and LDFRT. The patient will see the physician and have labs and imaging completed per Appendix I scheduling. Repeat imaging should include the same modality used at baseline. For example, if a baseline MRI was performed, a post-LDFRT-FOLFOX MRI should be repeated. If a baseline endorectal ultrasound (ERUS) was performed, a post-LDFRT-FOLFOX ERUS and CT scan should be repeated.

The decision to proceed to TME directly, or alternatively receive standard chemoradiation off protocol followed by TME, will be based on radiological and clinical tumor response.

Patients will proceed directly to TME unless any of the following occurs, at which time they will be discontinued from treatment on this study and be recommended to pursue appropriate treatment off-study.

- If there is any evidence of progressive disease (PD) by either imaging or clinical assessment.
- If a patient with radiologically measurable disease has an overall radiologic tumor response status of stable disease (SD).
- If a patient with disease that is not radiologically measurable has a clinical tumor response of 20% or less as determined by endoscopy.

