6.1.3.2 Acceptable modalities for measurable disease

- Conventional CT and MRI: This guideline has defined measurability of lesions on CT scan based on the assumption that CT slice thickness is 5 mm or less. If CT scans have slice thickness greater than 5 mm, the minimum size for a measurable lesion should be twice the slice thickness.
- For this study, when an MRI is performed, the technical specifications of the scanning sequences used should be optimized for the evaluation of the type and site of disease. The lesions should be measured on the same pulse sequence. Ideally, the same type of scanner should be used and the image acquisition protocol should be followed as closely as possible to prior scans. Body scans should be performed with breath-hold scanning techniques, if possible.
- PET-CT: The CT portion of the PET-CT can be used for RECIST measurements and can be used interchangeably with conventional CT in accurately measuring cancer lesions over time.
- Evaluation of disease by MRI is preferred. However, for patients who are not able to undergo an MRI or for clinicians who prefer it, an ERUS is acceptable. If ERUS is performed as an alternative to MRI at baseline, then an ERUS must also be performed at the time of restaging.
- In cases where ERUS is the modality selected to evaluate the primary rectal tumor, an accompanying CT for complete pelvic disease staging will also be interpreted by the on-site radiologist.
- A standard CT of the abdomen and pelvis or chest, abdomen and pelvis with oral and intravenous contrast is required. In the event that radiologic studies yield inconsistent interpretation of T stage or N stage the modality that assigns the highest T stage or the highest N stage should be used for purposes of protocol eligibility.

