8.2.2 Pathologic response other than a pCR

The definition of a non-pCR will include any surgical specimen that has any evidence of residual tumor manifest in the primary or regional lymph nodes.

For patients who do not meet criteria for a pCR, the extent of response to pre-operative therapy will be graded using the Tumor Regression Grade (TRG) schema that is included in the AJCC 7th edition. This was also used by Rodel in the pre/postoperative rectal cancer study and was subsequently adopted by the AJCC [Rodel (JCO 2005; 23:8688-8696)]. This schema evaluates the

degree to which the primary rectal tumor specimen has responded to neoadjuvant treatment.

Tumor regression grade (TRG)	Response categorization	Description
TRG 0	Complete	No viable cancer cells
TRG 1	Moderate	Single cells or small groups of cancer cells
TRG 2	Minimal	Residual cancer outgrown by fibrosis
TRG 3	Poor	Minimal or no tumor kill; extensive residual cancer

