12.0 PATIENT DISCONTINUATION

Patients may discontinue study treatment at any time. Any patient who discontinues treatment will be encouraged to return to the study center to undergo treatment discontinuation assessments. The primary reason for discontinuation should be documented.

Reasons for discontinuation of a patient by the investigator include, but are not limited to, the following:

- Documented disease progression or <20% clinical response to LDFRT-FOLFOX
- Symptomatic progression, characterized by increasing tenesmus or hematochezia, decreasing stool caliber, or other signs of imminent bowel obstruction.
- Patient not able or willing to complete the prescribed radiation therapy.
- Patient not able or willing to complete 6 cycles of neoadjuvant FOLFOX.
- Patient non-compliance.
- Patient withdraws consent to participate in the study.
- Persistent (≥ 3 weeks) NCI CTCAE version 4.0 grade 3-4 adverse event or any significant adverse event that compromises the patient's ability to participate in the study.
- Investigator determination that it is not in the patient's best interest to continue participation. It is the right and duty of the Investigator to interrupt the treatment of any subject whose health or well-being may be threatened by continuation in this study. Such subjects should be withdrawn from the study and referred for standard of care treatment.

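### Section 5.1.3 lets an MRI read after all six cycles make a patient ineligible, and with no stated pCR denominator that label permits an exclusion that depends on response

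*Combined protocol and SAP*

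**What the plan says.** The clause is in 5.1.3 of the combined protocol and SAP. It lists patients who are to have preoperative chemoradiation with infusional 5-FU: those who cannot tolerate six cycles, those needing a dose below level -2, those withdrawing consent, and "those who are found to be ineligible for the study based on central review of either the baseline or the follow up MRI". The stated consequence is a treatment route. The analysis is not mentioned.

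Other sections bear on the same patients:

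- **4.0 Registration:** "Patients can be registered only after all eligibility criteria are met". Appendix I dates the qualifying pelvic MRI or ERUS to at most 28 days before registration. No criterion in Section 3 refers to imaging after treatment.
- **6.0 Restaging:** patients with progression, radiologic stable disease, or a clinical response of 20% or less do not go straight to TME, "at which time they will be discontinued from treatment on this study and be recommended to pursue appropriate treatment off-study". Section 6.2.1.3 refers them for off-protocol chemoradiation and then TME.
- **12.0 Patient discontinuation:** an open list of reasons that includes "Documented disease progression or <20% clinical response to LDFRT-FOLFOX".
- **8.2:** pCR means no tumor in the specimen or nodes. Non-pCR covers "any surgical specimen that has any evidence of residual tumor". Neither definition mentions treatment given between LDFRT-FOLFOX and surgery.
- **Synopsis, 10.1 and 14.0:** the synopsis gives "Accrual Goal: 30 patients". Section 10.1 speaks of a total of 30 studied, and 14.0 of enrolling 30. None defines an evaluable population, a denominator or a replacement rule.

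The primary objective (2.1) asks whether the regimen "results in a pCR response rate of at least 35" percent.

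**The concern.** A scan taken after all protocol therapy cannot show whether a patient met entry criteria that had to be satisfied before registration. What it can show is how the tumor responded. Attaching the word ineligible to it therefore makes eligibility depend on outcome. The baseline half of the clause is different: a later central reading of the baseline scan can legitimately show that a registered patient never qualified.

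The label matters because nothing else in the plan tells the analyst what to do with these patients. Leaving ineligible patients out is common practice and would be a natural reading. Section 5.1.3 sends them to chemoradiation before surgery, so none can be a pCR after LDFRT-FOLFOX alone, and leaving them out raises the pCR rate attributed to the regimen. That rate is the primary estimate of a single-arm trial, and 14.0 says the results will be used to design the next study.

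A second gap lies beside the first. These patients may still reach TME, and 8.2.1 does not bar counting a pCR found there, although it would follow off-protocol chemoradiation.

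The clause also cannot be applied evenly. Section 6.1.3.2 accepts ERUS in place of MRI, and patients followed by ERUS fall outside it. Central review has no procedure or criteria anywhere else. For the CT that accompanies ERUS, the plan has "an accompanying CT for complete pelvic disease staging will also be interpreted by the on-site radiologist".

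**Working it through.** **1. Timing.** Six 14-day cycles put the last treatment at about week 10 and the end of cycle 6 at week 12. Restaging is 4 weeks ± 1 after completion, so the follow-up MRI falls at about week 13 (10 + 3) to week 17 (12 + 5) after the first dose. It is the only follow-up imaging in Appendix I.

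**2. The plan's own figures, all 30 counted.**

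- Early stop at a true rate of 5%: 0.95^9 = 0.630 (stated 0.63).
- Expected size: 9 + (1 − 0.630) × 21 = 16.76 (stated 16.76).
- Chance of passing = Σ over a = 1 to 9 of P(Bin(9,p) = a) × P(Bin(21,p) ≥ 4 − a). This is 0.0489 at p = 0.05 and 0.902 at p = 0.25 (stated error probabilities 0.05 and 0.10).
- Exact 95% interval for a 35% rate with n = 30: 0.186 to 0.545, width 0.359 (stated 0.36).

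All reproduce.

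**3. Exclusion without replacement.** The documents give no rate of follow-up-MRI ineligibility, so the removed fraction f of enrolled patients is an assumption. Every removed patient is taken as a non-pCR after LDFRT-FOLFOX alone. With true all-patient rate p:

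- pCRs: X ~ Bin(30, p)
- removed: K ~ Bin(30 − X, f/(1 − p))
- reported rate: X/(30 − K), with expectation p/(1 − f)

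At p = 0.25, the alternative in 10.1:

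| f | mean number removed | expected reported rate | chance of reporting ≥ 35% |
|---|---|---|---|
| 0 | 0 | 25.0% | 0.11 |
| 3.3% | 1 | 0.25/0.967 = 25.9% | 0.13 |
| 5% | 1.5 | 0.25/0.95 = 26.3% | 0.14 |
| 10% | 3 | 0.25/0.90 = 27.8% | 0.19 |
| 20% | 6 | 0.25/0.80 = 31.25% | 0.33 |

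At p = 0.27, the pilot rate cited in 1.3, the chance is 0.16 with all 30 kept, 0.27 at f = 10% and 0.43 at f = 20%.

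**4. In counts.** With 10 pCRs, 10/30 = 33.3% and 10/29 = 34.5%; two removals give 10/28 = 35.7%. With 9, five removals are needed (9/30 = 30.0% to 9/25 = 36.0%). With 8, eight are needed (8/30 = 26.7% to 8/22 = 36.4%). The exact intervals overlap heavily: 17–53% for 10/30 and 19–56% for 10/28.

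**5. Exclusion with replacement up to 30.** At a true all-patient rate of 5%, the rate among retained patients is 0.05/(1 − f). Putting this into the formula in step 2 gives a type I error of 0.057, 0.067 and 0.093 at f = 5%, 10% and 20%, against 0.049. No passage provides for replacement and none rules it out.

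**The case against.** The strongest reply is that 5.1.3 is a routing sentence under Chemotherapy. It groups these patients with those who cannot tolerate treatment or who withdraw, and it says nothing about who is counted. That is correct. A reader might infer that the clause, followed as written, removes patients from the 30. The text does not say so, and the enrolment wording in the synopsis, 10.1 and 14.0 points towards counting everyone. What remains is that nothing makes this binding.

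A reader might also infer that these patients cannot be pCRs at all. That is too strong. Section 6.2.1.3 refers patients with a poor restaging result for chemoradiation followed by TME, and 8.2.1 would admit a pCR there. The sound statement is limited to pCR after LDFRT-FOLFOX alone, and the attribution rule is itself missing.

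Nor is it established that 5.1.3 and the restaging rules describe one and the same event. Section 5.1.3 gives no criterion for an adverse follow-up MRI. Section 12.0 is not exhaustive and does not name radiologic stable disease, so it supports the discontinuation reading without being contradicted. The clear conflicts are with 4.0 and Section 3, and with how 6.0 and 6.2.1.3 class a poor restaging result.

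On size, the removal rates are assumptions, and the clause reaches only patients followed by MRI. One removal on average moves the expected rate by less than one percentage point, and a single removal cannot carry a result across 35%. The documents attach no formal decision rule to 35%. All of this stands, and it makes the point a modest one.

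**Conclusion.** The concern holds in a limited form. Section 5.1.3 contains a stated rule under which eligibility can turn on a post-treatment scan. That cannot be squared with 4.0 and Section 3, and it differs in status from the discontinuation described in 6.0 and 6.2.1.3. The clause does not by itself exclude anyone. Because 10.1 and 14.0 fix no denominator or replacement rule, it permits an exclusion that depends on response.

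The size is conditional on assumed removal rates and on every removed patient being a non-pCR after LDFRT-FOLFOX alone. At a true 25%, removing 3.3% to 20% inflates the expected rate by about 1 to 6 percentage points. The harm is to the primary estimate and its interval. The two-stage error rates (0.049, power 0.902) are unaffected without replacement. This is a cheap improvement, and it does not invalidate the design.

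**What to change.** In 5.1.3, limit ineligibility to findings on the baseline scan, and reconcile the status of patients with an adverse follow-up MRI with 4.0, 6.0 and 6.2.1.3. The treatment route is not at issue and should be left alone.

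In 10.1 and 14.0, state that:

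- follow-up imaging never removes a patient from the analysis set;
- the primary pCR denominator, at both the 9- and 30-patient looks, is one fixed set, namely all patients who start protocol treatment, without replacement;
- a patient who does not go directly from LDFRT-FOLFOX to TME counts as non-pCR, and any pCR after off-protocol chemoradiation is reported separately.

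Report two sensitivity analyses, with numbers and reasons: the rate among patients going directly to TME, and the rate excluding patients found ineligible on the baseline MRI.

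The cost is one clause and a few sentences, with no new data, visits or patients. The downside is that the headline pCR rate may be somewhat lower.
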